## **10.4 Primary objective**

The primary safety objective of this study is to report the effect of everolimus on height, BMI and sexual development (using Tanner Stages) in children and adolescents with TSC-associated SEGA who are taking everolimus or have taken everolimus.

### 10.4.1 Variable

To monitor the growth and the development of pediatric patients the following measurements will be performed annually:

- Height
- Weight
- Tanner Stage
- LH, FSH, and estrogen levels (female patients) starting age 10
- LH, FSH, and testosterone levels (male patients) starting age 10

#### 10.4.1.1 Statistical hypothesis, model, and method of analysis

#### 10.4.1.2 Height and BMI

The height standard deviation score (SDS) will be calculated based on height data collected during the study and published reference height information. The height SDS (also called z-score) will be computed for a particular patient at each time point. The same approach will be used to compute BMI SDS. BMI will be calculated as weight (in kg) / squared height (in m). The z-scores will allow identification of potential outliers.

SDS will be calculated using the current formulae provided by the WHO as follows:

1. Calculate  $z_{ind} = \frac{\left(\frac{X}{M}\right)^L - 1}{LS}$
2. If  $|z_{ind}| \leq 3$ ,  $SDS = z_{ind}$   
If  $z_{ind} > 3$ ,  $SDS = 3 + (X - SD3pos) / SD23pos$   
If  $z_{ind} < -3$ ,  $SDS = -3 + (X - SD3neg) / SD23neg$

where:

- $X$  is height in centimeters or BMI in kilograms/m^2,
- $L$ ,  $M$  and  $S$  are height or BMI-, sex- and age-specific reference values from the WHO Growth Charts.
- $SD3pos$  is the cutoff 3SD calculated by the LMS method:  
 $SD3pos = M * (1 + LS*3)^{1/L}$
- $SD3neg$  is the cutoff -3SD calculated by the LMS method:  
 $SD3neg = M * (1 + LS*(-3))^{1/L}$
- $SD23pos$  if the difference between the cutoffs 3SD and 2SD:  
 $SD23pos = M * (1 + LS*3)^{1/L} - M * (1 + LS*2)^{1/L}$
- $SD23neg$  if the difference between the cutoffs -2SD and -3SD:  
 $SD23neg = M * (1 + LS*(-2))^{1/L} - M * (1 + LS*(-3))^{1/L}$

Height-for-age and BMI-for-age L, M and S reference values for boys and girls are available under <http://www.who.int/childgrowth/standards/en/> (for patients aged between 0 to 5 years old) and <http://www.who.int/growthref/en/> (for patients aged between 5 to 19 years old). These correspond to the latest available international references available at the time of this protocol and described in the 2007 Bulletin of the World Health Organization ([Mercedes de](#)

Onis et al 2007). However these references may be revised according to new available standards at the time of the analysis.

The age category immediately above the patient's exact age should be used. SDS is actually a Z score that measures the distance from the population mean in units of standard deviations. That is,  $SDS < 0$  refers to values lower than the population mean, and for example  $SDS \leq -1.645$  refers to values in the lowest 5%. (The usual percentile more commonly used in the clinical practice can be derived from the Z-score by a normal distribution).

The time-course of height and BMI SDS will be summarized, side by side, on the FAS of the studies CRAD001M2305 and TOSCA using descriptive statistics by year since the enrollment date (for TOSCA patients) or since the start of everolimus (for CRAD001M2305 patients). The counts and frequencies of patients with height and BMI SDS values lower than the 5th percentile (notably low) or higher than the 95th percentile (notably high) will be described on the FAS, overall and by region.

The rate of height (respectively BMI) growth notable abnormality will be calculated as the rate of patients with a height SDS  $<$  5th percentile at the last time point where height is reported.

If a high rate of notably height (respectively BMI) growth abnormality occurs in the CRAD001M2305 patients, the relationship between the everolimus exposure and the height growth abnormality will be further explored as detailed below:

- The rate of height (respectively BMI) growth abnormality will be described in the different subgroups defined by the duration of everolimus exposure. These subgroups will be defined in the Report and Analysis Plan.
- The duration of exposure and the age at start of everolimus will be summarized using descriptive statistics in the subgroups of patients with and without a height (respectively BMI) growth abnormality.
- A logistic regression including the duration of exposure and the age at the start of everolimus as continuous covariates will also be used to further explore the relationship between the everolimus exposure and the height (respectively BMI) growth notable abnormality. Additional covariates (e.g. time normalized Cmin) might also be included in the model.

In addition, individual patient graphs for height and BMI over time will be provided for CRAD001M2305 patients.

#### **10.4.1.3 Tanner Stage**

Tanner Stage will include two components for boys, namely testis and pubic hair; and two components for girls: breast development and pubic hair.

Percentage of patients who will have reached Tanner Stage V by age 16 (for females) or age 17 (for males) will be provided, side by side, on the FAS Puberty of the studies CRADM2305 and TOSCA, along with 95% confidence intervals.

The relationship between the everolimus exposure and the Tanner Stage will be further explored in the CRAD001M2305 patients as detailed below:

- The percentage of patients who will have reached Tanner Stage V by age 16 (for females) or age 17 (for males) will be described in the different subgroups defined by duration of everolimus exposure. These subgroups will be defined in the Report and Analysis Plan.
- The duration of exposure and the age at start of everolimus will be summarized using descriptive statistics in the subgroups of patients who will reach and who will not reach Tanner Stage V by age 16 (for females) or age 17 (for males).
- A logistic regression including the duration of exposure and the age at the start of everolimus as continuous covariates may also be used to further explore if needed the relationship between the everolimus exposure and the achievement of Tanner Stage V by age 16 (for females) or age 17 (for males). Additional covariates (e.g. time normalized Cmin) might also be included in the model.

#### **10.4.1.4 Endocrine parameters**

Endocrine parameters such as LH, FSH, testosterone levels (in males) and LH, FSH, estrogen levels (in females) will be summarized descriptively, side by side, by gender and by age over time on the FAS of the studies CRADM2305 and TOSCA.

In addition individual patient graphs over time will be provided for the CRAD001M2305 patients.

All data will be listed.

#### **10.4.2 Handling of missing values/censoring/discontinuations**

All missing data will simply be described as missing on appropriate tables/listings in particular for patients who will not have reached Tanner Stage V or the age of 16 years (for females) or the age of 17 years (for males) at the end of the CRAD001M2305 study or at the end of the TOSCA registry using the FAS Puberty.

#### **10.4.3 Supportive analyses**

Not applicable

### **10.5 Secondary objectives**

The following secondary objectives will be described: the long term-safety, the age at Tanner Stage II-V, the age at thelarche and menarche for females, the age at adrenarche for males and the TAND Checklist responses.

Additionally an indirect comparison of CRAD001M2305 and TOSCA will be performed to compare the height, BMI and sexual development (using Tanner Stages).

#### **10.5.1 Safety objectives**

The secondary safety objective of the study will be based mainly on the frequency of adverse events. All safety data will be listed.

### **10.5.1.1 Analysis set and grouping for the analyses**

All listings and tables will be presented for all CRAD001M2305 patients using the Safety Set for adverse events.

The overall observation period will be divided into two mutually exclusive segments:

1. everolimus exposure period: from day of first commercial dose received in the M2305 study to 30 days after the last commercial dose received in the M2305 study.
2. post-everolimus exposure period:
  - starting at day 30+1 after the last commercial dose received in the M2305 study  
or
  - starting at the enrollment date for patients who will stop everolimus in M2301 and who will not start commercial everolimus.

### **10.5.1.2 Adverse events (AEs)**

Summary tables for adverse events (AEs) have to include only AEs that started or worsened during the everolimus exposure period, the treatment-emergent AEs. However, all safety data will be listed and those collected during the post-everolimus exposure period are to be flagged.

The incidence of treatment-emergent adverse events (new or worsening from baseline) will be summarized by system organ class and or preferred term, severity (based on CTCAE grades), type of adverse event, relation to everolimus treatment and by year since the enrollment date.

The prevalence over time of treatment-emergent adverse events will be described by system organ class and or preferred term.

Deaths reportable as SAEs and non-fatal serious adverse events will be listed by patient and tabulated by type of adverse event.

Clinically notable AEs (CNAE) will be considered. Such categories consist of one or more well-defined safety events which are similar in nature and for which there is a specific clinical interest in connection with everolimus.

For each CNAE, number and percentage of patients with at least one event part of the CNAE will be reported by categories regrouping the relevant preferred terms, as appropriate.

### **10.5.1.3 Other safety data**

The other secondary safety objectives of the study will be based on sexual and neuropsychological development data.

The age when patients reach each Tanner Stage II-V will be summarized on the FAS Puberty of the studies CRADM2305 and TOSCA.

The following variables will be summarized on the Safety Set (SS) (those are only collected in the CRAD001M2305 study) using descriptive statistics:

- age when females will start thelarche
- age when females will have their first menses
- age when males will reach adrenarche

For the age at which Tanner Stage II will be achieved, summary statistics from the Kaplan-Meier distribution will be determined on the FAS puberty, including the median age and the proportions of patients reaching this milestone at some given ages. These statistics will be given as point estimates with 95% confidence intervals. The same analyses will be performed for the following variables: age at which each Tanner Stage III, IV and V will be reached. Age at thelarche (females), age at menarche (females) and age at adrenarche (males) will be described similarly on the SS.

Potential delayed puberty will be defined based on Tanner stage and also on onset of menarche for girls. Potential cases identified through this algorithm, will be then clinically reviewed by assessing all available information in order to conclude the clinical relevance of the delay.

Potential delayed puberty in girls is defined as failure to attain Tanner Stage II (for both breast development and pubic hair) by age 13, or absence of menarche by age 15 or within 5 years of attainment of Tanner Stage II ([Fenichel 2012](#)) Potential delayed puberty in boys is defined as failure to attain Tanner Stage II (for both testis and pubic hair) by age 14 ([Traggiai 2002](#), [Tanner 1962](#))

Rates of potential delayed puberty will be described for boys and girls separately among the patients at risk of delayed puberty along with 95% confidence intervals. The patients at risk are patients who may potentially present an event of potential delayed puberty at baseline.

The rates of potential delayed puberty will be described in the different subgroups defined by duration of everolimus exposure. These subgroups will be defined in the Report and Analysis Plan.

The duration of exposure and the age at start of everolimus will be summarized using descriptive statistics in the subgroup of patients with potential delayed puberty.

If a high rate of potential delayed puberty occurs, a logistic regression including the duration of exposure and the age at the start of everolimus as continuous covariates will also be used to further explore the relationship between the everolimus exposure and the rate of potential delayed puberty. Additional covariates (e.g. time normalized Cmin) might also be included in the model.

These patients will be clinically reviewed by assessing all available information in order to evaluate their puberty development.

All responses to the individual questions from the TAND Checklist (collected in both studies) will be summarized using descriptive statistics on both studies, side by side, and over time on the FAS of studies CRAD001M2305 and TOSCA.

Safety data from other assessments will be listed, notable values flagged, and any other information collected will be listed as appropriate.

#### **10.5.1.4 Indirect comparison**

If the missing data pattern will not limiting, an indirect comparison between patients treated by everolimus (from CRAD001M2305 study) and those who never received an mTOR inhibitor (TOSCA subset of patients) will be performed to evaluate the everolimus effect on

growth and sexual development. Due to the observational nature of the TOSCA registry and its limited follow-up time, the statistical analysis will be primarily descriptive.

The following steps will be followed:

- The following non-exhaustive list of baseline characteristics will be used to assess potential imbalances between the two groups of patients: age at baseline, race, country, gender, age at first diagnosis of TSC, height abnormality at baseline, BMI abnormality at baseline, TSC mutation, type of TSC lesions, endocrine abnormality at baseline, Tanner Stage at baseline.
- If any imbalances that are deemed to affect the comparison of the two groups are identified in the step above, propensity scores will be calculated using the appropriate statistical model according to the observed missing data pattern. The propensity score is the conditional probability of being a member of one of the groups to be compared (i.e. probability of being from the CRAD001M2305 study) given the patient's covariates (D'Agostino 1998, Rosenbaum 1984).
- Strata defined by the propensity scores (e.g. quintiles) will be then created and the balance between the groups within those strata will be examined.
- If deemed relevant, the estimated propensity scores may then be used to obtain estimates for the effect of everolimus on growth (respectively sexual) development, through matching and/or logistic regression adjustment, using the CRAD001M2305 and TOSCA FAS (respectively FAS-Puberty) analysis sets. Matching will be considered if there is a much larger sample size of untreated (TOSCA) patients as compared to the CRAD001M2305 patients. In regression adjustment the propensity score may be included either as its raw score or as per the defined strata. In addition to the propensity score a subset of the other baseline characteristics covariates may be included.

The following should be noted: the above described use of propensity scores is exploratory and highly dependent on the observed data (observed imbalances between groups, observed missingness pattern) and therefore it is not possible to fully pre-specify all aspects of the planned analyses. In addition, whereas a formal randomization guarantees that there should be no systematic differences in observed and unobserved covariates between the groups to be compared, the propensity scores are conditional only on the observed covariates. Thus, even if the use of propensity scores is intended to reduce bias and increase precision of the treatment effect, these indirect comparisons analyses using the propensity score methodology will be considered exploratory only and should be interpreted with cautious.

For each covariate used to investigate the imbalances between the two groups (and then calculate the propensity score) the missing-data mechanism will be explored. If relevant (depending on the number of patients in the TOSCA Full Analysis Sets, amount of missing data, missing-data mechanism), specific methods like Multiple Imputation or ECM algorithms may be considered to estimate the propensity scores in presence of missing data. Handling of missing data is an evolving field of research and additional methods may be considered at the time of the availability of these long-term data. This will be further detailed in the Report Analysis Plan.

If the missing data pattern will not limiting, the effect of everolimus on height (respectively BMI) growth abnormality may also be assessed as an exploratory analysis through the use of

propensity scores in a logistic regression or matching comparison as detailed before. The same analysis will be performed for the achievement of Tanner Stage V by age 16 (for females) or age 17 (for males).

### 10.5.2 Pharmacokinetics

Blood trough levels collected at investigator discretion in compliance with local product information should be recorded, if available.

The time-normalized Cmin value will be estimated for the entire treatment period using recorded everolimus Cmin values and prescribed doses in that treatment period. Cmin will be summarized with descriptive statistics over time in the SS.

Time-normalized Cmin (Cmin,TN) will be calculated over each assessment interval (t1, t2). The time-normalized Cmin is defined as:

$$C_{min,TN} = (C_{min,t1} * p1 + C_{min,t2} * p2) / (p1 + p2)$$

- Cmin is considered to be the same within the same dosing interval (Cmin,ti is the mean Cmins if multiple Cmins are available within a dosing interval)
- The dosing interval Pi is number of days in which the patient is treated with the same dose (in mg).
- If there is no valid Cmin value available within a dose interval, the following imputation rule will be applied: the last Cmin,ti value will be taken and multiplied by the ratio of the dose given in the current dose interval to that of the previous dose interval.
- The dose refers to the prescribed dose.

If a high rate of growth/puberty abnormalities occurs, the potential relationships between Cmin and growth/puberty data will be explored in the SS as follow:

Percentage of patients who will have reached Tanner Stage V by age 16 (for females) or age 17 (for males) will be presented split by exposure to everolimus, in terms of patient's time-normalized Cmin. As per everolimus label the target Cmin for pediatric patients is between 5 to 15 ng/mL, the time-normalized Cmin will be categorized as < 5 ng/ml, 5-10 ng/ml and > 10 ng/ml. Note: if there are insufficient numbers of patients in one of the groups the categories may be collapsed.

The same descriptive analyses will be performed for the rates of potential delayed puberty and for rate of notably low BMI/height SDS.

### 10.6 Exploratory objectives

Not applicable

### 10.7 Interim analysis

No formal interim analysis is planned for this study. However, safety outputs may be generated for regulatory safety updates.

## 10.8 Sample size calculation

No formal sample size calculation has been performed in this non-comparative study which consists in the long-term safety follow-up of CRAD001M2301 paediatric patients. It is anticipated that approximately 50 patients who have participated in CRAD001M2301 would be eligible to enter CRAD001M2305.

Based on the safety findings in study CRAD001M2301 in terms of growth development where the estimated rate of patients with growth development abnormality was between 5 – 10% as of 11-Jan-2013 cutoff, it can be expected that the proportion of patients with growth development abnormality in this study would be in the same range, between 5 - 10%. The growth development abnormality would be defined as rate of notably low height SDS at the cut-off date of the analysis.

The proposed sample size of 50 patients will allow estimating a two-sided 95% confidence interval for rate of patients with growth development abnormality. [Table 10-1](#) below shows the exact binomial 95% confidence interval ([Clopper and Pearson 1934](#)) and the precision of the estimate for N=50 for various numbers of observed patients with growth abnormality. Note that the final interval will depend on the final sample size.

**Table 10-1 95% confidence interval for different number of observed patients with growth development abnormality during M2305 (sample size N = 50)**

Number of patients with growth development abnormality	Rate of patients with growth development abnormality	Exact binomial 95% confidence interval
0	0.00	(0.00, 0.07)
2	0.04	(0.00, 0.14)
4	0.08	(0.02, 0.19)
6	0.12	(0.04, 0.24)
8	0.16	(0.07, 0.29)
10	0.20	(0.10, 0.34)
12	0.24	(0.13, 0.38)
14	0.28	(0.16, 0.42)

With this sample size of 50, if we observe 4 patients with growth development abnormality (which corresponds to an observed 8% rate) there will be 79% probability of true rate of patients with growth development abnormality  $\leq 10\%$ . Probabilities that the true rate of patients with growth development abnormality is lower or equal to 10% with different number of observed patients with development abnormality are illustrated in [Table 10-2](#). These calculations are based on the binomial distribution.

**Table 10-2 Probability that the true rate of patients with growth development abnormality is lower or equal to 0.10 as a function of number of observed patients with development abnormality**

Number of observed patients with growth development delay	Observed rate of patients with growth development delay	P(true rate of patients with growth development delay $\leq$ 0.10   observed rate)
0	0.00	1.00
2	0.04	0.99
3	0.06	0.92
4	0.08	0.79
5	0.10	0.62
6	0.12	0.44
8	0.16	0.17
10	0.20	0.05

## 10.9 Power for analysis of key secondary variables

No power calculation was made for secondary analyses.

## 11 Ethical considerations and administrative procedures

### 11.1 Regulatory and ethical compliance

This clinical study was designed, shall be implemented and reported in accordance with the ICH Harmonized Tripartite Guidelines for Good Clinical Practice, with applicable local regulations (including European Directive 2001/20/EC and US Code of Federal Regulations Title 21), and with the ethical principles laid down in the Declaration of Helsinki.

### 11.2 Responsibilities of the investigator and IRB/IEC/REB

The protocol and the proposed informed consent form must be reviewed and approved by a properly constituted Institutional Review Board/Independent Ethics Committee/Research Ethics Board (IRB/IEC/REB) before study start. Prior to study start, the investigator is required to sign a protocol signature page confirming his/her agreement to conduct the study in accordance with these documents and all of the instructions and procedures found in this protocol and to give access to all relevant data and records to Novartis monitors, auditors, Novartis Clinical Quality Assurance representatives, designated agents of Novartis, IRBs/IECs/REBs and regulatory authorities as required.

### 11.3 Informed consent procedures

Eligible patients may only be included in the study after providing written (witnessed, where required by law or regulation) IRB/IEC/REB-approved informed consent, or, if incapable of doing so, after such consent has been provided by a legally acceptable representative of the patient. In cases where the patient's representative gives consent, the patient should be informed about the study to the extent possible given his/her understanding. If the patient is

capable of doing so, he/she should indicate assent by personally signing and dating the written informed consent document or a separate assent form.

Informed consent must be obtained before conducting any study-specific procedures (i.e. all of the procedures described in the protocol). The process of obtaining informed consent should be documented in the patient source documents. The date when a subject's Informed Consent was actually obtained will be captured in their CRFs.

Novartis will provide to investigators, in a separate document(s), proposed informed consent form(s) (ICF) that are considered appropriate for this study and complies with the ICH GCP guideline and regulatory requirements. Any changes to this ICF suggested by the investigator must be agreed to by Novartis before submission to the IRB/IEC/REB, and a copy of the approved version must be provided to the Novartis monitor after IRB/IEC/REB approval.

Women of child bearing potential should be informed that taking the study medication may involve unknown risks to the fetus if pregnancy were to occur during the study and agree that in order to participate in the study they must adhere to the contraception requirement for the duration of the study. If there is any question that the patient will not reliably comply, they should not be entered in the study.

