## 2 Rationale

### 2.1 Study rationale and purpose

The results from [CRAD001M2301] have shown that a significant proportion of patients with advanced TSC-associated SEGA benefited from continuous treatment with the mTOR inhibitor everolimus which led to volume reduction of the SEGA lesions. Patients with TSC-associated SEGA are typically young children at pre-pubertal age whose physical and sexual maturation is ongoing. mTOR has been shown to be an important regulator of cell growth and proliferation. Additionally, it is possible that mTOR is also a regulator of sexual development and maturation. As many patients treated in [CRAD001M2301] were young at the time of their exposure to everolimus (an mTOR inhibitor) and/or have experienced prolonged exposure to the drug from a young age, patients exposed to everolimus as part of CRAD001M2301 may present an appropriate study population in which to track the long term impact of everolimus exposure on growth and development.

Upon request by the EMA (during the procedure EMEA/H/C/002311/II/0004), this safety extension-study, classified as Post-Authorization Safety Study (PASS), is implemented to continue growth and development monitoring of pediatric patients enrolled in CRAD001M2301 who have been treated or are being treated with everolimus.

The study will monitor the growth and development of pediatric patients with TSC-associated SEGA, previously enrolled in CRAD001M2301 until they reach Tanner Stage V, or until age 16 for females or 17 for males whichever occurs first. After completion of [CRAD001M2301] continued treatment with everolimus is at investigator discretion and is not required for participation in CRAD001M2305. It is expected that some patients will cease treatment with everolimus upon completion of study CRAD001M2301, but most will opt for continued treatment with everolimus. Under either circumstance, the patients will be eligible for enrolment in study CRAD001M2305.

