# 5 Population

## 5.1 Patient population

The target population is comprised of pediatric female and male patients who have previously participated in the study [CRAD001M2301] and have not, prior to enrollment into CRAD001M2305, reached age 16 for females, or age 17 for males. Additionally, these patients will not yet have achieved Tanner Stage V. Study treatment in study [CRAD001M2301] must have been completed within 6 months prior to enrollment into CRAD001M2305.

The investigator or designee must ensure that only patients who meet all inclusion are offered participation in the study. No additional exclusions can be applied by the investigator, in order that the study population will be representative of all eligible patients. All screening assessments must be completed and reviewed by the investigator (or designee) prior to starting study participation in CRAD001M2305.

All pediatric study patients and their parent(s) or legal guardian must be thoroughly informed about all aspects of the study, including the study visit schedule and required evaluations, and all regulatory requirements in order to ensure informed consent. The written informed consent must be obtained prior to performing any CRAD001M2305 study procedures. If the patient is unable to read, an impartial witness and/or the patient's parent or legal guardian must be present during the entire informed consent discussion. The following criteria apply to all patients enrolled into the study.

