## 5.2 Inclusion criteria

Patients eligible for inclusion in this study have to meet **all** of the following criteria:

1. Pediatric female patients who were on study treatment in study [CRAD001M2301] within the past 6 months and have not reached Tanner Stage V or age 16 at the time of

completion of [CRAD001M2301]  
or

2. Pediatric male patients who were on study treatment in study [CRAD001M2301] within the past 6 months and have not reached Tanner Stage V or age 17 at the time of completion of [CRAD001M2301].
3. Written informed consent according to local guidelines.

Tanner Staging results that were obtained and documented within 6 months prior to enrollment into CRAD001M2305 may be used for enrollment decisions.

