### 5.3 Exclusion criteria

1. Pediatric female patients who were on study treatment in CRAD001M2301 and have not reached Tanner Stage V but are within 3 month of turning age 16  
or
2. Pediatric male patients who were on study treatment in CRAD001M2301 and have not reached Tanner Stage V but are within 3 months of turning age 17
3. Any patient who was pregnant prior to start of CRAD001M2305

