## 6 Treatment

This study does not require treatment with any medication.

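### Protocol 11.3 makes contraceptive compliance an entry bar that the eligibility criteria do not list, in a monitoring study that requires no drug

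*Protocol*

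**What the plan says.** The last paragraph of Protocol 11.3 does three things for women of childbearing potential.

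- It has them told that "taking the study medication may involve unknown risks to the fetus".
- It has them "agree that in order to participate in the study they must adhere to the contraception requirement for the duration of the study".
- It closes with an instruction to the site: "If there is any question that the patient will not reliably comply, they should not be entered in the study".

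Eligibility is set elsewhere. Section 5.2 asks for treatment in the parent study within the past 6 months, limits on age and Tanner stage, and "Written informed consent according to local guidelines". Section 5.3 excludes patients within 3 months of the age limit and "Any patient who was pregnant prior to start of CRAD001M2305". Neither section mentions contraception. Section 5.1 adds: "No additional exclusions can be applied by the investigator, in order that the study population will be representative of all eligible patients".

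On the drug, Section 6 states: "This study does not require treatment with any medication". Section 2.1 says that "continued treatment with everolimus is at investigator discretion and is not required for participation in CRAD001M2305", and that patients who stop are eligible as well as those who carry on.

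**The concern.** The 11.3 paragraph reads like consent text from a drug trial, where the sponsor supplies the product and can refuse patients for whom its fetal risk cannot be managed. This study only observes growth and puberty. Any everolimus is commercial and prescribed under the local label.

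Followed as written, the closing sentence can keep an otherwise eligible girl out of height, BMI, Tanner and hormone monitoring for a reason that has no bearing on monitoring. It applies only to girls judged to be of childbearing potential, a term the protocol does not define. Whether the bar applies to a girl may therefore depend on how far through puberty she is. The study reports age at menarche, potential delayed puberty and attainment of Tanner Stage V by 16, so entry could be selected on something close to the outcome.

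**Working it through.** No arithmetic applies. The check is to set the texts side by side.

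1. **Is it an instruction or background?** An instruction. It says who should not be entered. Under 11.2 investigators sign to follow all the protocol's instructions, and Section 12 permits no authorized deviations, so a site cannot simply treat it as inert.

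2. **Is it among the listed criteria?** No. It is absent from 5.2, from 5.3, and from the criteria in the protocol summary. The agreement to use contraception could be regarded as part of consent, which is the third inclusion criterion. The closing sentence cannot, because it turns on the site's doubt about future behaviour. A girl and her parents can consent fully and still be refused.

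3. **Does it fit the stated population?** Poorly. Section 4.1 says the study takes all consenting pediatric patients who meet the age, Tanner and recent-treatment conditions. Section 5.1 wants a population that represents all eligible patients. Section 11.3 itself begins from patients who are already eligible, and its last sentence then removes some of them on the site's judgement.

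4. **Does its reason fit the study?** No. The reason given is the risk of taking a study medication. Section 6 requires none, the protocol summary marks investigational therapy as not applicable, and 2.1 admits patients off everolimus. The period also does not match: adherence is asked for throughout the study, but under 7.1.3 patients who stop everolimus stay in the study, so time in the study can exceed time on the drug.

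5. **Whom can it reach?** Section 11.3 states no on-drug limit. Section 7.2.2.7 refers to situations in which effective contraception is required and points to the local label. Read through that section, the requirement may concern only girls taking commercial everolimus. Read alone, 11.3 covers any girl of childbearing potential. On either reading the pool is narrow, because girls at Stage V, aged 16, or within 3 months of 16 are already ineligible.

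6. **Is there evidence of intent?** Amendment 1 records, as item 4 of its list of changes, that wording implying mandatory everolimus treatment was removed from Sections 2.1, 6, 7.1.3, 10.3 and 10.4 and from Figure 4-1. Section 11.3 is not in that list. This shows only the direction in which the sponsor was editing. It suggests that 11.3 was overlooked.

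7. **Can an effect be sized?** No. The documents do not say how many eligible girls were judged to be of childbearing potential, how many were doubted on contraception, or how many were refused.

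**The case against.** The strongest reply has four parts.

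First, 5.1 forbids exclusions added by the investigator, whereas 11.3 is the sponsor's own text, and many protocol criteria call for investigator judgement. This stands as a literal reading. A reader might infer that 11.3 flatly contradicts 5.1, but the wording of 5.1 does not go that far. What remains is a conflict with the aim stated in 5.1, with the inclusive wording of 4.1, and with the place where eligibility is defined.

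Second, the requirement can be read as applying only to girls on everolimus, for whom 7.2.2.7 says the drug is not recommended without contraception. That reading is coherent and removes the problem for girls off the drug. For girls on it, the remedy in the label concerns the prescription. It gives no reason to withhold monitoring, and the bar is still unlisted.

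Third, strictness about pregnancy risk at entry is not odd in itself, since 5.3 already excludes patients pregnant before the start. This also stands. A reader might infer that the protocol is harsher on doubt about contraception than on pregnancy, because 7.2.2.7 continues monitoring after a pregnancy during the study. That sets an entry rule against an in-study rule, and at entry pregnancy is excluded too.

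Fourth, no consequence is shown. That is correct. The consent form is a separate document that was not supplied, so the wording families received is unknown.

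**Conclusion.** The point holds as a minor inconsistency of design wording. Section 11.3 contains an operative entry bar that the eligibility sections omit. Its rationale does not fit a study that requires no drug, and it works against the inclusive population described in 4.1 and 5.1.

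This rests on reading the closing sentence as an instruction to sites, and it holds whether the bar reaches all girls of childbearing potential or only those on commercial everolimus.

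No size or direction of bias is claimed, and the effect may be zero. Three further inferences are tempting and unsupported:

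- A reader might infer that girls were in fact refused, or that the clause explains low enrollment. No document records a refusal or links enrollment to 11.3.
- A reader might infer that the bar favours earlier or later maturers. With childbearing potential undefined, the direction cannot be determined. A girl of 15 without menarche could be covered under one definition and not under another.
- A reader might infer that deletion has no safety cost at all. One advisory step at entry would go, although the label and 7.2.2.7 still cover the matter.

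**What to change.** In 11.3, delete the last sentence and the clause that makes contraceptive adherence a condition of taking part. Keep the fetal-risk information, addressed to girls taking commercial everolimus, and refer to the local label on contraception as 7.2.2.7 already does. Add one sentence stating that contraceptive compliance does not affect eligibility for monitoring. The exclusion in 5.3 of patients pregnant before the start stays as it is.

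While enrollment is open, this costs a wording change in the protocol and, if it carries the same text, the consent form.

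If enrollment is closed, which the January 2024 SAP amendment ahead of the final database lock suggests, the remedy is one sentence in the CSR. It should say whether any eligible girl is known to have been refused for this reason, or else name the clause as a possible source of selection. The answer may be incomplete: under 6.3.1 a patient number is assigned only on signing consent, so a girl turned away before that may have left no study record.
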